PSM Misuse and Co-occurrence of AOD. We have consistently shown that PSM misuse is also a marker for heavy AOD involvement as it seldom occurs in isolation^{1, 145-147}. Students who engage in PSM misuse are at risk for a host of issues related to alcohol and marijuana use compared to those who do not use PSM and those who use but do not misuse (i.e., take the PSM as prescribed), including being more likely to have used other drugs, to report frequent binge drinking, and more likely to drive after binge drinking than other college students^{4, 29-30, 33, 36-37, 131}. Adolescents and young adults have particularly high rates of concurrent poly-drug use with up to 90% of past-year PSM misusers reporting using other drugs, particularly marijuana^{31, 33-35}. Students who misuse PSM are more likely to meet diagnostic criteria for dependence on alcohol and marijuana, and are more likely than students abusing other drugs to report any drug related problems and to experience nine out of ten drug related consequences as assessed by the Drug Abuse Screening Test-10 (DAST-10)³²⁻³³. Thus, in addition to harm related to PSM misuse per se, considerable harm is related to the co-occurrence of PSM misuse with excessive alcohol, marijuana, and other drug use.

Dearth of Interventions and Missed Opportunities. Given the prevalence and consequences of PSM misuse on college campuses, the high co-occurrence with alcohol and marijuana, and the academic and public health implications, innovative prevention and treatment approaches are critically necessary^{14, 20, 33, 39-41}. However, there are currently *no documented efficacious interventions* targeting college students who misuse PSM. The proposed study explicitly leverages expert knowledge ([name]) from existing NIDA-funded research on risk factors for PSM with expertise in screening and brief intervention (SBI) for college student alcohol and marijuana misuse by leaders in the field ([name], [name], [name], [name], [name]) to develop and test such an intervention on three college campuses, in order to attack the problem of PSM misuse and bridge this important research and service gap. Consistent with other interventions in the college setting, we propose to

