4) Perceived norms and AOD as theoretical mediators: We have completed 5 RCTs evaluating efficacy of computer/internet delivered PNF for alcohol use among college students^{93-95,142}. Consistent with our proposed research hypotheses, drinking reductions in all studies were mediated by changes in perceived norms for the typical student, providing additional support for the correction of normative misperceptions as an active theoretical mechanism for intervention efficacy. [name] and colleagues¹⁴³ also investigated the impact of norm misperception on illicit drug use. 5990 participants provided information on use, perceptions, and consequences of marijuana use. Two-thirds of participants reported no marijuana use, but 98% of respondents incorrectly predicted the "typical student" used marijuana at least once per year. Estimates of peer use and use by the typical student each added significantly to separate equations predicting variance in drug use and in related consequences. [name] has collected preliminary data at UAlbany supporting misperceptions of the norm for PSM misuse. Specifically, students were asked "Within the last school year, do you think the typical student at your school used any of the following prescription drugs (for stimulants) that were not prescribed to him/ her?" Results indicated 74% of students perceived that the typical student used stimulants within the last year, though the actual rate of use on that campus was reported at 25%. Drs. [name] and [name] recently published a paper on normative misperceptions of PSM¹⁵⁶. Their research similarly found that students overestimated PSM misuse by other students and those normative estimates were associated with student's own higher PSM use. Living in a fraternity or sorority was related to higher PSM use and perceived norms. Finally, higher normative perceptions were associated with higher hazardous drinking. Thus, our preliminary studies and bio-sketches demonstrate our ability to successfully conduct this research.

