
Study 2 Baseline and Randomization: The web-based screening survey will automatically generate an eligibility determination. Students who are ineligible will be shown a message thanking them for their interest in the study and directing them to campus resources that are available to them if they wish to discuss AOD issues. Those meeting the eligibility criteria above will automatically be directed to complete the baseline assessment measures. Once baseline is completed, students will be randomly assigned to either an intervention group (PFI) or assessment only control (AOC) group. Those in the intervention will immediately receive online personalized feedback (see below) on their PSM misuse, academics, and links to alternatives. Over the course of the quarter/semester, students in the intervention group will receive a link to view 4 additional modules surrounding PSM misuse, AOD use, Consequences, and Beliefs/Motives about PSM use. The AOC group will receive a "thank you" screen providing referrals/emergency numbers. Students will be assessed at 6, 12 and 18 months post-baseline using similar email invitations and reminders (expected retention 90% based on past research). Participants will be paid \$20, \$25, and \$30 for each follow-up survey. Students who indicate significant alcohol or drug dependence will be contacted and referred (See Human Subjects). We will make any indicated adjustments/refinements to feedback based on findings prior to *Study 3*.

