Aim 1: To examine whether perceived norms of PSM differs from the “actual” prevalence as estimated by the screening sample, the actual prevalence will be subtracted from the perceived prevalence. A one-sample t-test will be used to assess whether the difference score is statistically significantly greater than 0. If the difference score is a non-normal distribution, we will instead use a non-parametric Wilcoxon sign rank test.

Aim 2: Evaluate efficacy of interventions. We will first examine effects of the intervention on perceived norms, benefits of PSM, and use of alternative strategies as separate outcomes using linear mixed models (a.k.a. hierarchical linear or multilevel models¹²⁰). This project will have 5 repeated measures, yielding up to 6,000 Level 1 observations (repeated-measures) across 1,200 Level 2 (people). The following equation represents a basic analytic model for Aims 2 and 3:

$$\text{Level 1: } Y_{ti} = \pi_{0i} + \pi_{1i}(\text{Post})_i + \pi_{2i}(\text{Month6})_i + \pi_{3i}(\text{Month12})_i + \pi_{4i}(\text{Month18})_i$$

$$\text{Level 2: } \pi_{0i} = \beta_{00} + \beta_{01}(\text{Tx})_i + \beta_{02}(\text{Site})_i + r_{00i}$$

$$\pi_{1i} = \beta_{10} + \beta_{11}(\text{Tx})_i + \beta_{12}(\text{Site})_i$$

$$\pi_{2i} = \beta_{20} + \beta_{21}(\text{Tx})_i + \beta_{22}(\text{Site})_i$$

$$\pi_{3i} = \beta_{30} + \beta_{31}(\text{Tx})_i + \beta_{32}(\text{Site})_i$$

$$\pi_{4i} = \beta_{40} + \beta_{41}(\text{Tx})_i + \beta_{42}(\text{Site})_i$$

where *Post*, *Month6*, *Month12*, and *Month18* are dummy codes for follow-up visit such that the reference time point is baseline; *Tx* represents randomly assigned treatment condition; *Site* represents the study site; *i* indexes participants; *r_{00i}* represents a random effect for the intercept; and *Y_{ti}* represents the outcome for each individual, *i*, at each time, *t*. $\beta_{11} - \beta_{41}$ are primary coefficients as they compare treatment conditions for the difference in the outcomes from baseline to each of the follow-up visits. The model assumes conditional independence, given random-effects and (multivariate) normality of Level 2 random-effects. As additional analyses, we will also specify time as a continuous variable in order to assess differences between intervention and control groups in slopes over time.

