We will then examine effects on PSM, marijuana, and alcohol use and consequences. These outcomes are integers, bounded at zero, and often times positively skewed. Because of potential violations of regression assumptions that can arise due to the non-normal distribution, we will use a generalized form of the linear mixed model (GLMM) with a Poisson distribution in order to more appropriately model these outcomes as counts¹¹⁷. Count regression coefficients are connected to the outcome via a natural log link and are commonly exponentiated (e^β) to yield rate ratios (RRs) describing the proportional increase in the outcome for a 1-unit increase in the predictor (e.g., Treatment (1) compared to Control (0)).

To assess mediation hypotheses, we will utilize an approach that has been used by co-investigators with similar data to the proposed study¹⁹⁷. Kenny et al.¹⁹⁸ described mediation using multilevel models for longitudinal treatment data similar to the present data. Specifically, Kenny et al. focused on change in the direct treatment pathways from a model without the mediator to a model with the mediator (i.e., the common c and c' pathways in the mediation literature). In the present context, that is the treatment cross-level interactions with time ($\beta_{11} - \beta_{41}$) for the model presented above compared to one in which mediators are included as Level 1 time-varying covariates. We will use this approach and consider the percent reduction in effects after the mediator is included in the model. In Neighbors et al¹⁹⁹, this approach was extended using a nonparametric bootstrap¹⁹⁹ to allow estimation of the indirect path without making normality assumptions on the sampling distribution of the indirect effect. Perceived benefits and norms of PSM, use of alternative strategies, and alcohol and marijuana use will be included as the Level 1 time-varying mediators of interest and PSM use and consequences will be modeled as the outcomes. To assess moderators of efficacy, we will include level 2 covariates for baseline levels of motivations of PSM and demographic characteristics as well as their interactions with treatment in the GLMM.

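### The mediation model enters mediators uncentred, with no person-mean term, so stable differences between students can appear as mediation in both Study 2 and Study 3.

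*Combined protocol and SAP*

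**What the plan says.** The Aim 2 model has visit dummies at Level 1 and treatment and site at Level 2. Its only student-level random term is r00i, which "represents a random effect for the intercept". PSM use and consequences are modelled as Poisson counts with a log link.

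For mediation, β11–β41 from that model are compared with those from "one in which mediators are included as Level 1 time-varying covariates". The team will "consider the percent reduction in effects after the mediator is included in the model", and a nonparametric bootstrap is described for the indirect path. The mediators "will be included as the Level 1 time-varying mediators of interest and PSM use and consequences will be modeled as the outcomes".

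No section states a person mean, centring, a within/between split, a baseline-mediator term, or the timing of mediator relative to outcome. The plan cites methods papers for the approach but does not report what they say on these points.

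The section on in-person feedback in the health and counseling centers hypothesises the same mediators for Study 3. Aim 3 reuses the basic model with arm dummies and gives no separate mediation method.

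The number of waves is stated in two ways. Aim 2 says "This project will have 5 repeated measures, yielding up to 6,000 Level 1 observations", while Study 2 Baseline and Randomization says "Students will be assessed at 6, 12 and 18 months post-baseline", which with baseline makes four. Both counts are used below.

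**The concern.** A random intercept is assumed independent of the covariates, so it does not remove stable differences between students from a raw time-varying covariate. The single mediator slope becomes a weighted blend of the between-student association and the within-student effect. The drop from c (treatment-by-time coefficient without the mediator) to c′ (with it) is roughly that slope times the treatment effect on the mediator. Randomisation protects c but not the mediator slope, and a bootstrap puts an interval around the blended quantity without correcting it.

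Two conditions are needed, and the documents point to both:

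- **Treatment moves the mediator.** This is hypothesised throughout the Significance section. Preliminary/Pilot Studies reports d = .61–.96 on normative perceptions in the team's earlier alcohol-feedback trials.
- **The stable mediator level is related to stable misuse.** For norms: "Living in a fraternity or sorority was related to higher PSM use and perceived norms". For alcohol and other drugs: "PSM misuse is also a marker for heavy AOD involvement as it seldom occurs in isolation". The section on beliefs and perceptions reports a similar link for perceived benefits.

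At stake are the mediation hypotheses in both studies. An inert component could be reported as an active mechanism, and a real one could be overstated.

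**Working it through.** **1. The plan's own figures.** 5 × 1,200 = 6,000 observations, as stated. exp(−.30) = .741, matching the stated rate ratio of .74. exp(−.13) = .878 against the stated .87, a small rounding gap. Power above .80 cannot be reproduced, because the Power section gives no intercept or random-effect variance. As an approximation, SE = √[(3 + exp|b|)/(n × mean count)]:

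- Study 2: √[(3 + 1.139)/(600 × 3.2)] = .0464, and .13/.0464 = 2.80, which is power .80.
- Study 3: √[(3 + 1.350)/(100 × 3.79)] = .107, and .30/.107 = 2.80, which is power .80.

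Mean counts near 3.2 and 3.8 are therefore compatible with the stated power, but they are inferred, not documented.

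**2. Set-up.** Counts were generated with a within-student mediator effect of zero, so true mediation is 0%. A Poisson random-intercept model was fitted by maximum likelihood without the mediator, with it as written, and with it split. Apparent mediation = (c − c′)/c over follow-ups. From the plan: 600 per arm with −.13 (Study 2), and three arms of 100 with −.30 (Study 3). Assumed:

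- Set A: mean count 3 (Study 2) or 5 (Study 3), random-intercept SD .8, within-student log-rate SD .3, mediator intraclass correlation .5.
- Set B: mean count 3.2 or 3.8, random-intercept SD .8, mediator intraclass correlation .6.

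**3. Mechanism (set B, student-level correlation .5, mediator shift −.61 SD).**

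| Study, waves | Slope | Slope × shift | Simulated c − c′ | Share of c |
|---|---|---|---|---|
| 2, five | .0766 | −.0467 | −.0472 | .0472/.13 = 36% |
| 2, four | .0944 | −.0576 | −.0578 | .0578/.13 = 44% |
| 3, five | .0730 | −.0445 | −.0448 | .0448/.30 = 15% |
| 3, four | .0910 | −.0555 | −.0556 | .0556/.30 = 18.5% |

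The true slope is zero in every row. The log-scale bias is nearly the same in the two studies. Only the denominator differs.

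**4. Size under set A, correlations .3 and .5.**

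| | Shift .2 SD | Shift .61 SD |
|---|---|---|
| Study 2 | 5.0 and 8.9% (five waves); 6.8 and 11.4% (four) | about 15–35% over both wave counts |
| Study 3 | 1.8 and 2.8% (five waves) | about 5–10% |

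**5. How often it would be seen.** Set A, five waves, .2 SD: the participant-bootstrap 95% interval for c − c′ excludes zero in 68% (correlation .3) and 88.5% (.5) of Study 2 data sets, and in 14.5% for Study 3 (.5). Set B, .61 SD, correlation .5: a simulated 95% interval for the indirect path excludes zero in 100% of Study 2 data sets, and in 82.5% (five waves) and 92% (four) for Study 3.

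**6. Checks.** Under set A, if treatment does not move the mediator, apparent mediation is 0.1% and the interval excludes zero in 6%. If the student-level correlation is zero, it is −0.2%. Set B agrees.

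**7. Sensitivity (set B, Study 2, five waves, .61 SD, correlation .5).** 74% at mean count 1 and 15% at mean count 8. 45% and 29% at random-intercept SD .4 and 1.2. 20% and 66% at mediator intraclass correlation .4 and .8.

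**8. With the split.** Apparent mediation is within 0.7 of a percentage point of zero in the repeated-data-set runs under both sets. With true mediation of 50% and correlation .5 (set A, shifts .2 and .35 SD), the model as written gives 58% and 64%, and the split gives 50% and 49%.

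**The case against.** - **The cited papers may specify centring.** They may, but they are not in the documents, and the written model is what an analyst would follow. A reader might infer that the team chose an uncentred mediator deliberately. The text shows only that nothing else is stated.
- **The association evidence comes from general student samples.** This stands. Only current misusers are enrolled, and the restricted range may shrink the student-level correlation. Its size in this trial is unknown.
- **The size depends on the inputs chosen.** This stands. The sensitivity runs go from 15% to 74%, so no single figure should be read as a forecast.
- **There is no decision rule to inflate.** This is partly right. The plan considers the percent reduction and estimates an indirect path; it sets no threshold. The interval rates above show how a routine reading would turn out. The percent reduction is biased with or without a threshold.
- **The person mean contains post-randomisation values.** This is true, but the mean is constant over time and barely alters the treatment-by-time coefficients. The unadjusted β11–β41 can remain the reported total effect.
- **The split does not deal with reverse causation.** This stands. When misuse drives the mediator (within-student correlation .3 and .5), the split shows 9% and 25% apparent mediation, against 8% and 22% unsplit. That limits the wording of results; it is no reason to keep a removable bias.

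**Conclusion.** The concern holds for both studies. As written, the analysis can report mediation where there is none, provided treatment moves the mediator and stable mediator level is related to stable misuse. The spurious part is a larger share of the smaller Study 2 effect and is detected more often with 1,200 students. Study 3 is not exempt: its bias looks negligible only if the mediator is assumed to move little, and the team's own earlier trials report larger shifts for norms.

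The ranges rest on assumed mean counts, random-intercept SD, mediator intraclass correlation and student-level correlation. They establish that the bias can be material, not what this trial will find.

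Two stronger readings are not supported. A reader might infer that the efficacy results are compromised, but β11–β41 without the mediator are randomised comparisons and are untouched. A reader might also infer that the mediation findings will be false. The documents do not give the quantities needed to say so.

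The change should be made before the mediation analysis is run. It does not bear on the efficacy tests.

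**What to change.** For both studies, state in the mediation paragraph that:

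1. Each mediator enters as two terms: the student's own mean over waves, and the deviation from that mean at each wave.
2. The percent reduction rests on the deviation term. Compare β11–β41 between a model with the person mean only and a model with the mean plus the deviation.
3. The bootstrapped indirect effect uses the same term and resamples participants. The comparison model matters: in Study 2 at .2 SD, the split interval wrongly excluded zero in 9.5–10.5% of data sets (correlations .3 and .5) when c came from the model without the person mean, and in 5.8% and 5.0% when it came from the model with it.
4. The unadjusted β11–β41 remain the reported total effects.
5. The timing of mediator and outcome is given, and same-wave results are worded as associations that do not establish direction. The plan's own section on alcohol and marijuana comorbidity describes stimulants enabling longer drinking, which is the reverse path.

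The cost is SAP wording and a few lines of code, with no new data. In the runs with true mediation of 50%, the split detected it as often as the model as written (82% each). It removes stable confounding only; time-varying confounding and reverse causation remain.

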In Person Feedback in Student Health and Counseling Centers. With well documented barriers related to implementing approaches developed in a lab setting or in the context of a research trial to “real world” clinical settings, Study 3 will test the efficacy of the PFI in a Student Counseling and Health Center at a large, diverse public university in the Northeastern U.S. Students presenting with medical and/or mental health concerns will be screened for PSM misuse as well as AOD use as part of their routine care and will be offered either an in-person session, the web-based PFI, or assessment only control based on random assignment. For practical purposes related to staff time in a busy clinical setting, web-based PFI, if effective with this population, would be preferable; however, if in-person PFI outperforms the web-based (or only under certain conditions for certain students), this will help identify how to best serve students who may be struggling. An important aspect of our in-person approach will be to use the student’s past experiences with PSM as a starting point. An MI-trained interventionist will help the student to develop discrepancies, elicit change talk, provide students with opportunities to more thoroughly explore and question their beliefs, and offer alternatives by reviewing their personalized responses. MI has been an effective approach for other interventions, and it is an appropriate modality for this target population. Thus, **Study 3** aims to determine whether and for whom in-person implementation of the PFI is more efficacious than web-based PFI in reducing PSM misuse and co-occurring alcohol and marijuana use. We hypothesize both web- and in-person PFI will be more efficacious than control. We also hypothesize in-person intervention will be more efficacious than web, particularly at long-term follow-up (18-months), given some literature suggesting advantages of in-person PFI emerge over longer periods²⁰⁰. As with Study 2, we expect reductions in perceived benefits and norms of PSM and increases in alternative behaviors will mediate efficacy of both interventions, as will reductions in alcohol and marijuana use. We will explore demographics and PSM motives as moderators of overall and differential efficacy.

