Study Methodology Overview: The proposed RCT aims to examine the efficacy of a PFI for reducing PSM misuse. Study 1 will document normative perceptions on each of the 3 participating campuses. Study 2 will examine the efficacy of a web-delivered PFI adapted and expanded from models like BASICS which will contain tailored information on normative misperceptions of PSM misuse, contrasting commonly held misconceptions about the benefits of PSM with research-based information about the actual effects of PSM, and learning and study strategies as alternatives to PSM misuse compared to a control condition, as well as components targeting comorbid alcohol and marijuana misuse. For Study 3, an in-person individually-delivered PFI (adapted from web format to face-to-face) addressing PSM and AOD misuse will be compared to the web-delivered PFI tested in Study 2 and to an assessment only control. The two studies will evaluate outcomes with respect to both short-term (6 months) and longer-term (12 and 18 months) reductions in four substance-related outcomes: (a) the perceived norms and benefits of PSM misuse, (b) PSM misuse frequency, (c) marijuana use frequency, and (d) alcohol use frequency and quantity.

Setting: Participants will be recruited from three universities: The University of Washington (UW), the University of Maryland College Park (UMCP), and University at Albany, State University of New York (UAlbany). UW is located in Seattle, WA and UMCP is located nine miles from Washington DC, with each school's total undergraduate enrollment of more than 30,000. UAlbany, which is one of four SUNY University Centers, is classified as a Research II and NCAA Division I institution with more than 12,000 undergraduate students. All three universities are coeducational and very diverse with regard to race, ethnicity, religion, gender, age, disability, and sexual orientation.

Studies 1 & 2 Recruitment Procedures: A total of 8,172 undergraduates for Study 1 and 15,732 for Study 2 aged 18 to 24 (age restricted in order to maintain comparability with prior SBI/PFI interventions with college students) will be randomly selected from the University Registrars' databases across the 3 sites. Students will be emailed an invitation to log on to a secure web browser, read a consent statement and indicate their willingness to participate in the study. Approximately 50% of invited students will respond to the invitation (Study 1 N=4,086 and Study 2 N=7,866).

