Study 3 Recruitment, Randomization & Assessment Procedures: All students who present for services at the University at Albany Health Center and University Counseling Center will be invited to complete a brief, web-based assessment of their PSM and AOD (identical to *Study 2*) in order to assess eligibility for *Study 3* before meeting with their service provider. Routine screening is already part of ordinary clinical practice at UAlbany Health and Counseling Centers, and annually more than 1300 unique individuals visit these centers and complete routine screening. Our own pilot data suggests more than 2/3 of heavy illicit substance users make at least one visit to a campus health clinic annually, indicating these settings are ideal for identifying non-treatment-seeking at-risk PSM users. During the student's medical or counseling appointment, the provider will review the Screening Questionnaire and will refer eligible students to the study using a referral script similar to ones from prior studies successfully conducted in this setting. The same eligibility criteria will be used: students must have misused PSM once or more in the past month and/or 6 or more times in past year.

Students agreeing to participate in the study will be emailed an invitation to log onto a secure web browser,

read a consent statement and indicate their willingness to participate in the study. Those indicating their consent will immediately be routed to the baseline survey which will be used to generate the web-delivered or in-person PFI content and for which they will receive \$20. Following baseline, participants will be randomly assigned to one of three conditions (n = 100 per condition). For Study 3, students will be randomly assigned to either a web-delivered PFI (as in Study 2), a one-session face-to-face brief intervention delivered in an MI style using the PFI as generated in the web condition, or an assessment only control group.

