Aim 3: Efficacy of in-person and web-based interventions. GLMM Poisson regression will be also used to test the efficacy of the web-based PFI and in-person MI on reducing PSM use and consequences. Using the basic model equation, dummy variables rather than a single treatment indicator will be included as Level 2 covariates for web-based PFI and in-person MI such that the reference will be the control group. In addition to comparisons of the two intervention groups to the control, we will also conduct post-estimation general linear contrasts to compare effects of the web-based PFI and in-person MI on the PSM outcomes.

Missing data and attrition. Our prior research has been successful at retaining participants with 85-93% retention over 6 months or longer. GLMMs provide unbiased estimates in the presence of missing data as long as it can be considered ignorable. Missing data are ignorable if they are either missing completely at random or missing at random after accounting for measured variables in analysis, including outcome at earlier time

points¹²⁰. As seen in previous studies, little efficiency is lost in GLMMs with 10%-20% missing data.

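### The Aim 3 model's only setting term, Site, is constant in single-campus Study 3, so recruiting center (Health or Counseling) goes unadjusted; replacing Site with center is a cheap improvement

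*Combined protocol and SAP*

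**What the plan says.** Under Data Analysis, Aim 2, the plan writes out a two-level equation and gives it a double purpose: "The following equation represents a basic analytic model for Aims 2 and 3". Its only setting covariate is Site, which "represents the study site" and appears in the intercept equation and in each of the four visit-slope equations (β02 to β42). The Setting paragraph says what the sites are: "Participants will be recruited from three universities".

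Aim 3 carries the equation over to Study 3 with one stated change: "Using the basic model equation, dummy variables rather than a single treatment indicator will be included as Level 2 covariates". Nothing is said about Site.

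Study 3 recruits on one campus through two centers: "All students who present for services at the University at Albany Health Center and University Counseling Center will be invited" (Study 3 Recruitment, Randomization & Assessment Procedures). The contact may be either a "medical or counseling appointment, the provider will review the Screening Questionnaire". The Significance section describes the same intake: "Students presenting with medical and/or mental health concerns will be screened for PSM misuse as well as AOD use as part of their routine care".

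Recruiting center is not named as a randomization stratum, as a covariate, or among the moderators (motives and demographic characteristics, including fraternity/sorority status). The nearest provision is a follow-up question on other drug treatment sought since the intervention, collected to control for confounding. It is not in the Aim 3 equation.

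**The concern.** The plan considered setting important enough to let both the baseline level and every visit-specific change differ by Site. In Study 3 that protection disappears without comment, because Site takes one value. The setting contrast that does exist there, medical versus counseling intake, is not put in its place.

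The two groups could plausibly follow different courses over 18 months. A random intercept absorbs a stable difference in level between them, but not a difference in change, and the treatment coefficients of interest are all differences in change. With 100 students per arm, a chance excess of Counseling Center clients in one arm would carry their trajectory into that arm's contrast. At stake are some precision in the smaller of the two trials and protection against an unlucky allocation. An analyst would also have to decide after the fact what, if anything, replaces Site.

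**Working it through.** **Inputs from the plan.** Study 3 has 100 students per arm, 300 in total, and five measurement occasions (baseline, post, months 6, 12 and 18). The Power section states power of .80 or higher for a coefficient of −.3, given as a rate ratio (RR) of .74, at p < .05 (two-sided assumed).

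**Inputs assumed, because the plan gives none.** The share p from the Counseling Center is 30% to 50%. The effect of center on change in use at follow-up is RR 0.7, a log effect of ln(0.7) = −.357. Assignment is taken as unstratified by center, since the plan says only that it is random.

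**1. The plan's figure.** exp(−.3) = .741, which agrees with the stated .74. The power itself cannot be reproduced, because the simulation's intercept and random-effect variance are not reported. Power of exactly .80 implies a standard error of .3/(1.960 + .842) = .107, used below.

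**2. Estimability of Site.** The fixed part has five time columns (intercept and four visit dummies), each crossed with two treatment dummies and Site: 5 + 10 + 5 = 20 columns. With Site constant, its five columns are either zero or copies of the time columns. The computed rank is 15, so all five Site coefficients are inestimable. With center added the design has 25 columns and rank 20. Removing the five redundant Site columns leaves 20 columns at full rank, so center can be estimated where Site cannot.

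**3. Chance imbalance between two arms of 100.** SD = √(2p(1−p)/100).
- p = .30: √.0042 = .065; 95% limit 1.96 × .0648 = .127.
- p = .50: √.0050 = .071; 95% limit 1.96 × .0707 = .139.

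**4. Shift in the treatment log RR** (imbalance × .357).
- Typical (1 SD): .0648 × .357 = .023; .0707 × .357 = .025. This is about 2%.
- At the 95% limit: .127 × .357 = .045; .139 × .357 = .050. This is 4–5%.

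**5. Gain from adjustment.** The share of contrast variance removed is (1-SD shift/.107)².
- p = .30: (.0231/.107)² = 4.7%.
- p = .50: (.0252/.107)² = 5.6%.
- Power becomes Φ(.3/(.107 × √(1 − .047)) − 1.96) = .82, and the same to two decimals at 5.6%.

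**6. Sensitivity.** For shares of 20–50% and center RRs of 1.25 to 2.0, the variance removed runs from 1.4% to 21%, and nominal power from .805 to .88.

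**7. Simulation check.** This was a simplified set-up: one follow-up, two arms of 100, baseline-adjusted Poisson regression with robust standard errors, 50% counseling, and 1,500 runs per scenario.

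| Scenario | Without center | With center |
|---|---|---|
| Center RR 1.5: mean estimate (true −.3) | −.300 | −.300 |
| Center RR 1.5: power | .742 | .782 |
| Center RR 1.5: type I error | .058 | .061 |
| No center effect: power | .775 | .773 |
| No center effect: type I error | .076 | .078 |

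The simplified test is somewhat liberal with or without center, so the comparison between columns is what matters. Omission caused no bias, and adjustment cost almost nothing when center was irrelevant.

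**The case against.** A reader might infer that the Aim 3 model cannot be fitted. That goes too far. The redundant Site terms drop out, and the treatment-by-visit coefficients, which the plan calls primary, remain estimable and unchanged.

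A reader might also infer that omitting center biases the Study 3 comparisons. It does not in expectation, because assignment is random. Chance imbalance is part of ordinary sampling error, and the simulation shows no bias and no material change in type I error.

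The mechanism is open to challenge too. The documents do not describe usual care by center, do not say that Counseling Center clients go on receiving counseling, and allow one student to have both medical and mental health concerns. That care differs by center is therefore an inference, and center is an imperfect proxy for it. The share and the RR of 0.7 are assumed, and at those values the gain is modest.

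The plan also shows some thought about concurrent care through its question on other drug treatment. That is a partial provision only. It concerns drug treatment rather than counseling in general, is measured after randomization and so could be affected by arm, and does not record where the student was recruited.

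Finally, a center-by-treatment analysis would tell little. With an even split, the interaction has about twice the main-effect standard error, so it would need a coefficient near −.6 (RR about .55) for the same power. These objections limit the size of the point. They do not show that Site does anything in Study 3 or that center is handled elsewhere.

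**Conclusion.** The point holds as a cheap improvement. The written Aim 3 model contains five setting coefficients that cannot be estimated and so has no working setting adjustment, although Study 3 draws from two distinct settings. If Site was meant to be re-read as center in Study 3, the text does not say so. The validity of the planned contrasts is not in question. The loss is modest precision and protection in the single trial that will be run: under the assumed share and RR of 0.7, about 5% of the contrast variance. It would be smaller if the centers follow similar courses and larger if they differ strongly.

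**What to change.** In the Aim 3 model, replace Site with recruiting center (Health = 0, Counseling = 1, recorded at referral) in the intercept and each visit slope. State how a student who uses both centers is coded, for example by the center that made the referral. If enrolment is not complete, stratify randomization by center; if it is complete, the analysis change is still worth making. A center-by-treatment analysis is optional and should be labelled exploratory, given its low power.

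The cost is a line in the SAP, a two-level stratum in the randomization, and five nuisance terms, the same number of terms as the equation already has.
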